10.2 Handling of the Difference Between the Scheduled and the Actual Sampling Times

The actual clock time for dosing and the actual clock time for each collection time for the efficacy/PD samples will be recorded using the electronic data capture. For all sampling times, the actual sampling times will be calculated as the difference between the sample collection actual clock time and the actual clock time of dosing. The actual post-dose sampling times expressed in hours and rounded off to three decimal digits will be used to calculate the efficacy/PD parameters, except for pre-dose samples occurring prior to dosing, which will always be reported as zero (0.000), regardless of the time difference. Scheduled sampling times will be presented in concentration tables and mean figures, while actual sampling times will be presented in the figures of individual results in the PK section of the report. A listing of the actual times will be provided for efficacy/PD samples.

10.3 Efficacy/Pharmacodynamic Parameters

A total of 10 blood samples will be drawn from each subject for efficacy/PD analyses. Blood samples will be collected on Day 0, Day 1, Day 3, Day 7, Day 14, Day 28, Day 35, Day 42, Day 84, and Day 112.

RVNA will be used to calculate the following parameters by standard non-compartmental methods:

AUEC_{0-t}: area under the effect-time curve above the minimum rabies virus neutralizing activity threshold (0.5 IU/mL) from time 0 to the last measurable concentration, calculated using the linear trapezoidal method. Unit will be Day*IU/mL.

AUEC₀₋₇: area under the effect-time curve above the minimum rabies virus neutralizing activity threshold (0.5 IU/mL) from time 0 to 7 days, calculated using the linear trapezoidal method. In case where the 7 days RVNA value is missing, AUEC₀₋₇ will be interpolated at the discretion of the pharmacokineticist. Unit will be Day*IU/mL.

- AUEC₀₋₁₄: area under the effect-time curve above the minimum rabies virus neutralizing activity threshold (0.5 IU/mL) from time 0 to 14 days, calculated using the linear trapezoidal method. In case where the 14 days RVNA value is missing, AUEC₀₋₁₄ will be interpolated at the discretion of the pharmacokineticist. Unit will be Day*IU/mL.
- AUEC_{14-t}: area under the effect-time curve above the minimum rabies virus neutralizing activity threshold (0.5 IU/mL) from time 14 days to the last measurable concentration, calculated using the linear trapezoidal method. In case where the 14 days RVNA value is missing, AUEC_{14-t} will be interpolated at the discretion of the pharmacokineticist. Unit will be Day*IU/mL.
- AUEC₁₄₋₃₅: area under the effect-time curve above the minimum rabies virus neutralizing activity threshold (0.5 IU/mL) from time 14 days to 35 days, calculated using the linear trapezoidal method. In case where the 14 days or 35 days RVNA value is missing, AUEC₁₄₋₃₅ will be interpolated at the discretion of the pharmacokineticist. Unit will be Day*IU/mL.
- E_{max}: maximum observed effect. Unit will be IU/mL.
- T_{max,E}: time of observed E_{max}. Unit will be Day.

Some efficacy/PD parameters may not be calculated for all or some subjects, at the discretion of the inVentiv pharmacokineticist, if the concentration data is not deemed to be amenable to evaluation. Explanations for efficacy/PD parameters that could not be estimated will be provided in the CSR.

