**Table 2.2-1 Treatment Allocation**

Treatment Allocation	Number of subjects
RVi + RIG	40
RVa + RIG	40
RVi + SYN023 0.3 mg/kg	40
RVa + SYN023 0.3 mg/kg	40
Total	160

The RVi and RVa regimens for post exposure prophylaxis are both five dose regimens. The initial dose of RVi and RVa will be co-administered with Study Drug (either RIG or 0.3 mg/kg SYN023) on Study Day 0. Rabies virus neutralizing activity (RVNA) and blood levels of SYN023 will be measured for the remainder of the trial while the rest of the post-exposure RVi and RVa doses are given. It is anticipated that RVNA will remain high during RVi and RVa administration and through the end of the study at Study Day 112. Pharmacodynamic efficacy will be defined as RVNA measured above 0.5 IU/mL with RVi and RVa for the duration of the trial and no more than 10% lower for SYN023 compared to RIG at any time point through Study Day 35. SYN023 concentrations and anti-SYN023 antibodies will also be measured.

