### **7.7 Sample Size Considerations**

The sample size for this Phase 2 study was selected based on requirement to consider noninferiority of the efficacy parameter, RVNA. The power analysis was performed in SAS 9.2 using the power procedure for noninferiority testing under the assumption of the sample size of 40 per group and likely margin corresponding to SYN023 being no less than 10% lower than RIG. Based on earlier studies, the mean RVNA for 0.3 mg/kg SYN023 of 20 with CV of 15-25% are reasonable. For assumed underlying differences of 0 to 1 IU/mL, there is over 80% to conclude non-inferiority of RVNA level at a specified time point. The sample size of 40 per treatment group should be sufficient to address the efficacy objectives of the study.

The assumptions that a difference of 2 or less is considered unimportant (the approximate mean value for 0.3mg/kg SYN023 of 20 was used), with the range in mean difference from -1 to 1, standard deviation of 3 and power of 0.8, the required sample size of 29 is needed to declare that the new treatment (SYN023) is not more tolerably inferior to the previous treatment (RIG). Also, the power analysis was performed for the sample size of 40, standard deviation 3 and the mean difference of 2. This resulted in the power of 0.838. The above results from the sample size and power analysis showed that the sample size of 40 should be sufficiently powered for this study.

Also, a power analysis for non-inferiority of the AUCs was performed using “PowerTOST”, an R CRAN package run under Rstudio version 0.99.491. Under the assumption of a lower non-inferiority bound of 0.9 (corresponding to SYN023 being no less than 10% lower than RIG), the selected sample size of 40 per group would provide over 80% power assuming a CV of 10-20%.

If no SAEs are observed among subjects in each dose group and the 40 subjects in the 3 dose groups combined, the one-sided exact upper 95% confidence bounds on the rate of SAE occurrence will be 45% and 18%, respectively.

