3.4 Subject Withdrawal and Replacement

Subjects were advised that they were free to withdraw from the study at any time. Over the course of the study, the Sponsor and Investigator or a delegate had the right to withdraw any subject from the study for one of the reasons described below; subject withdrawal will be done in accordance with inVentiv's SOP:

- Safety reason;
- non-compliance with protocol requirements;
- significant protocol deviation;

Subjects who withdraw or are withdrawn from the study after dosing will not be systematically replaced. Subjects who fail to complete the study through Study Day 28 may be replaced at the discretion of the sponsor.

4. Changes From the Protocol

For efficacy/PD analyses, AUC_{0-last} was replaced by $AUEC_{0-t}$, $AUC_{14-last}$ was replaced by $AUEC_{14-t}$, C_{max} was replaced by E_{max} , and T_{max} was replaced by $T_{max,E}$. This is standard nomenclature for such efficacy/PD parameters.

AUC_{0-inf} was removed from Efficacy/PD analyses because elimination phase cannot be calculated for rabies virus neutralizing activity (RVNA).

5. Primary and Secondary Parameters

The primary parameters will be $AUEC_{0-t}$ calculated on RVNA measured above 0.5 IU/mL. All other PD parameters will be regarded as secondary parameters (refer to Sections 10).

The safety, immunology and PK parameters will be regarded as secondary (refer to Sections 9, 11, and 12).

6. Analysis Populations

The analysis of safety and tolerability parameters will be based on the safety population detailed in Section 6.1 below. The analysis of immunogenicity (anti-SYN023 antibodies), PK, and PD parameters will be based on the Per-Protocol population detailed in Section 6.2 below.

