6.2 Per-Protocol Population

The PP population will consist of all randomized subjects who received all scheduled doses of a study treatment and remained on study for at least 28 days without major protocol violation. Treatment allocation will be based on as treated principle.

7. Interim Analyses

A review of Rabies Virus Inhibitory Activity, anti-SYN023 antibodies, SYN023 PK information and clinical safety data will be conducted following completion of Study Day 42. This review may present individual and aggregate (mean, median or 95% CI, as appropriate) and change from pre-study drug to each post administration time point by individual or in aggregate. Study procedures and monitoring practices will not change following this preliminary review. No decision cut points or stopping rules will be stipulated. No hypothesis testing will be performed. The purpose of this review is to obtain preliminary data for use in the decision-making process regarding Study Drug dose level. Personnel at the research site and at the immunology laboratory will remain blinded to all study results and to treatment assignments until after the Study Day 112 data have been collected, reviewed and queries resolved.

8. Study Population and Exposure

Shells for all summary descriptive statistic tables and listings referred to in this section are displayed in a separate document; the shells may be revised as they are presented to illustrate the general layout of data to be included in the final report.

No inferential analyses will be done.

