10.4.1 Similarity Acceptance

Using GLM procedures in SAS[®], ANOVA will be performed on untransformed $T_{\max,E}$ and ln-transformed $AUEC_{0-t}$, $AUEC_{0-7}$, $AUEC_{0-14}$, $AUEC_{14-t}$, $AUEC_{14-35}$, and E_{\max} at the alpha level of 0.05. Factors incorporated in the model will include: Vaccine, IG, and Vaccine*IG. Vaccine, IG, and Vaccine*IG will be tested against the residual mean square error. In the case of a non-statistically significant Vaccine*IG interaction term, the analysis will be rerun excluding this term from the ANOVA model in order to obtain ratios and confidence intervals where appropriate. In the case of statistically significant Vaccine*IG interaction term, the analysis will be rerun for each vaccine separately. All sums of squares (Types I, II, III and IV) will be reported. Probability (p) values will be derived from Type III sums of squares. Coefficients of variation (CV%) will be estimated.

Based on pairwise comparisons of the ln-transformed $AUEC_{0-t}$, $AUEC_{14-t}$, and E_{\max} data, the ratio (RIG/SYN023) of the geometric least-squares means, calculated according to the formula “ $e^{(X-Y)} * 100$ ”, as well as the corresponding 90% geometric confidence intervals will be determined.

For $AUEC_{14-t}$, a statistically significant Vaccine*Conmed interaction term will be interpreted as a possible interference of RIG or SYN023 on the vaccines. In this case, each vaccine will be investigated separately.

Additional analyses may be performed.

Criteria for Similarity

Considering PP population, the 90% geometric confidence intervals of the ratio (RIG/SYN023) of least-squares means from the ANOVA of the ln-transformed $AUEC_{0-t}$ must be within 80.00% to 125.00%.

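### The primary area AUEC0-t has no common end day, so a per-protocol subject last sampled before Day 112 can enter the similarity test with a truncated area

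*SAP*

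**What the plan says.** - SAP 5 makes AUEC0-t the primary parameter. SAP 10.3 defines it as the "area under the effect-time curve above the minimum rabies virus neutralizing activity threshold (0.5 IU/mL) from time 0 to the last measurable concentration". AUEC14-t is open-ended in the same way; AUEC0-7, AUEC0-14 and AUEC14-35 have fixed windows.
- SAP 10.4.1 sets one similarity criterion: "Considering PP population, the 90% geometric confidence intervals of the ratio (RIG/SYN023) of least-squares means from the ANOVA" of ln AUEC0-t must lie within 80.00% to 125.00%. If the vaccine-by-immune-globulin interaction is not significant, "the analysis will be rerun excluding this term from the ANOVA model in order to obtain ratios and confidence intervals where appropriate". The default comparison is therefore 80 v 80.
- SAP 6.2 requires all scheduled doses and that the subject "remained on study for at least 28 days without major protocol violation". SAP 3.4 draws the replacement line at the same day: "Subjects who fail to complete the study through Study Day 28 may be replaced at the discretion of the sponsor".
- SAP 14 allows observed data only, without extrapolation or interpolation, although SAP 10.3 permits interpolation for some areas.
- SAP 10.3 also says "Some efficacy/PD parameters may not be calculated for all or some subjects, at the discretion of the inVentiv pharmacokineticist", with an explanation in the CSR for parameters that could not be estimated.
- Protocol 2.2 anticipates that "RVNA will remain high during RVi and RVa administration and through the end of the study at Study Day 112".

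**The concern.** If RVNA is still high at the last visit attended, the end of the area marks when sampling stopped, not when the response ended. The last vaccine dose is due on Day 28. A subject who leaves after it can meet the per-protocol definition with four of the ten RVNA samples (Days 35, 42, 84, 112) and 84 of the 112 days still to come. One missed Day 112 sample, without withdrawal, shortens the area in the same way.

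Two things are at stake. Truncated areas spread out the ln-AUEC distribution, which costs power. If they are more frequent in one immune-globulin arm, they also move the RIG/SYN023 ratio itself: more RIG truncation lowers it, and more SYN023 truncation raises it.

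The exposure comes in with the SAP. Protocol 7.3 ran the similarity ANOVA on AUC0-inf. SAP 4 dropped that parameter because no elimination phase can be calculated, and no common end day was put in its place.

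**Working it through.** **Planned figure.** Neither document gives a power figure for 80-125% on AUEC0-t, so there is none to reproduce. The nearest is Protocol 7.7, for AUC non-inferiority with a bound of 0.9: "the selected sample size of 40 per group would provide over 80% power assuming a CV of 10-20" (per cent). That is a different test. I use only its CV range.

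**Inputs.** From the documents: the SAP 10.3 sampling days, the 0.5 IU/mL threshold, the linear trapezoid, 80 per arm, the 90% CI and its limits, CV 20% (top of the protocol's AUC range), and RVNA on Days 1/3/7 of 2.70/3.68/4.44 (0.3 mg/kg row of Protocol Table 1.5-1).

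Assumed:
- RVNA from Day 14 to Day 112 is flat at 20, falls log-linearly from 40 to 10, or falls from 20 to 2 IU/mL. Results are in that order.
- Leavers' last samples are spread evenly over Days 28, 35, 42 and 84.
- CV 40% serves as a sensitivity value. The Phase 1 Day 35 entry, 1.82 ± 0.93, would be a CV of 0.93/1.82 = 51% if ± is an SD, which the protocol does not state.

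**Step 1, share of the area captured.** Area = Σ (yᵢ + yᵢ₊₁)/2 × Δt, with y = max(RVNA − 0.5, 0). Flat profile, Days 0-14: 1.10 + 5.38 + 14.24 + 82.04 = 102.8. Adding 19.5 × 14 gives 375.8 at Day 28; adding 19.5 × 98 gives 2013.8 at Day 112. The share is 375.8/2013.8 = 19%.

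| Last sample | AUEC0-t share | AUEC14-t share |
|---|---|---|
| Day 28 | 19/30/40% | 14/24/31% |
| Day 42 | 32/48/59% | 29/43/54% |
| Day 84 | 73/85/92% | 71/84/91% |

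**Step 2, variance.** With exit share p and captured fraction f, the ln-scale variance is s² + p·E[(ln f)²] − (p·E[ln f])², where s² = ln(1 + CV²). Flat profile, CV 20%, p = 0.05: 0.0392 + 0.05 × 1.519 − (0.05 × 1.124)² = 0.1120, an observed CV of 34%. The three profiles give 34/28/25%.

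**Step 3, bias.** The ln ratio shifts by (p_RIG − p_SYN023)·E[ln f], with E[ln f] = −1.124/−0.763/−0.555. For 10% RIG v 5% SYN023 exit the ratio is multiplied by exp(0.05 × E[ln f]) = 0.945/0.963/0.973. A true 1.25 is then estimated at about 1.18/1.20/1.22. The reverse imbalance moves it up by the same factors.

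**Step 4, chance of meeting 80-125%.** Simulation of 40,000 trials per cell, two-arm 90% CI on the ln scale, 80 v 80. Entries can move by about one point between runs.

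| Scenario | CV 20% | CV 40% |
|---|---|---|
| True ratio 1, no leavers | 100% | 95% |
| True ratio 1, 5% exit in each arm | 98/99.9/100% | 81/90/92% |
| True ratio 1, 10% in each arm | 90/99/99.9% | 67/83/89% |
| True ratio 1, 10% v 5%, either direction | 86/98/99.8% | 64/81/88% |
| True ratio 1.25, equal exit | 5% | 5% |
| True ratio 1.25, 10% RIG v 5% SYN023 | 24/19/16% | 17/13/11% |
| True ratio 1.25, 5% RIG v 10% SYN023 | about 1% or less | 1-2% |

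If the interaction is significant (about 5% of trials by chance) each vaccine is analysed at 40 v 40. At CV 20% and 5% equal exit the chance of passing is then 79/94/98%, against 99.9% with no leavers.

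**The case against.** The strongest reply is that safeguards exist. The pharmacokineticist may leave an area uncalculated and must explain it. By-visit ratios (SAP 10.4.2), AUEC14-35 and disposition by arm (SAP 8.1) would show a problem. Protocol 2.2 and 7.3 also carry a separate criterion, that SYN023 be no more than 10% lower than RIG at any time point through Day 35; exit after Day 35 does not touch it, and a SYN023 deficit of 20% in that period would breach it. So it would be wrong to infer that the plan has no evaluability provision, or that a true deficit would pass unseen.

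What remains is narrower. The discretion has no stated criterion, and the CSR explanation covers areas that were not estimated, not truncated areas that were kept. SAP 10.4.1 does not use the by-timepoint criterion, and SAP 10.4.2 attaches no acceptance limit to its ratios. Major protocol violation is undefined; if leaving after Day 28 counted as one, the 28-day minimum would serve no purpose.

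A reader might also infer that the plan inflates false similarity. The documents do not support that. Equal exit leaves it at 5%, and inflation needs more exit under RIG. Subjects and the investigator are blinded (Protocol 3.4), subjects must have no plans to move (3.2.3), and missed visits are rescheduled where possible (3.6.5). Unequal exit is hypothetical, and the opposite imbalance makes false similarity rarer.

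**Conclusion.** The definitional point holds on the text: followed as written, the rules allow truncated areas into the primary comparison, and AUEC14-t shares the defect. The weight is minor to should-fix.

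At CV 20% and modest equal exit the pooled power loss is small. At CV 40% it is visible, from about 95% to 81-92% with 5% exit. If every leaver has a Day 84 sample, the loss at CV 20% is negligible even at 10% exit. Bias in the ratio matters only if exit differs by arm. All sizes rest on the assumed profiles, exit shares, exit timing and CV, none of which the documents settle.

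**What to change.** 1. Make AUEC0-112 the primary similarity parameter, with AUEC14-112 in place of AUEC14-t, and apply 80.00-125.00% to AUEC0-112.
2. Replace case-by-case discretion with one rule: no sample in the Day 112 visit window means not evaluable for these two areas.
3. Add one end-of-window rule. The Day 112 window is ±11 days (Protocol Table 3.1-1) and SAP 10.2 uses actual times, so completers may end anywhere from Day 101 to Day 123. Stopping at Day 101 captures 89/95/97% of the area. Either interpolate to Day 112 when the last sample is later and apply one stated short extension when it is earlier, or assign the in-window sample to nominal Day 112. Amend SAP 14 to permit this, and reconcile it with the interpolation clauses in SAP 10.3.
4. State that a BLQ value at Day 112 enters as zero and that the descending segment counts. From 10 IU/mL at Day 84 to 0 at Day 112 the line crosses 0.5 after 26.6 days, adding 9.5 × 26.6/2 = about 126 Day*IU/mL, which AUEC0-t omits.
5. Report AUEC0-42 under the same end-of-window rule, with its ratio and 90% CI, as supportive, and give the number not evaluable by arm.

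The cost is SAP wording and minor programming, with no new visits or samples. With 10% excluded from each arm (72 v 72), exit unrelated to response and true ratio 1, the chance of passing is 100% at CV 20% and about 93% at CV 40%; false similarity at a true ratio of 1.25 is 5%. These runs do not test the end-of-window rule.

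The downside is that exclusion assumes exit is unrelated to response. If exactly the top 8 of 80 RIG responders leave, with 5% random exit under SYN023 (CV 20%, true ratio 1.25), false similarity is about 35% with exclusion against 30/26/22% for AUEC0-t. For AUEC0-42 it is about 15%, assuming the same relative response there. AUEC0-42 should therefore be read beside the primary result.

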10.4 Statistical Analyses

Individual and mean RVNA versus time curves will be presented using linear and semi-log scales for RVNA. Listings and descriptive statistics (number of observations, arithmetic mean, SD, coefficient of variation [CV%], median, Min, Max, geometric mean, and the percentage of subjects with RVNA values above 0.5 IU/mL [% > 0.5 IU/mL]) of the RVNA versus time as well as all PD parameters will be provided for each treatment.

For inferential analyses, data will be analysed as a two-factor factorial design. The two factors will be Vaccine including 2 levels (RVi and RVa) and Conmed including 2 levels (RIG and SYN023) as described in Table 10-1.

Table10-1: Two-factor factorial design with Vaccine and Immune Globulin (IG) as factors

		IG	
		RIG	SYN023
Vaccine	RVi	N _A =40	N _C =40
	RVa	N _B =40	N _D =40

Where N_X is the number of subjects planned to be dosed for Treatment X (X=A, B, C, D).

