### **ANALYSIS OF EFFICACY**

RVNA of >0.5 IU/mL will be used as a pharmacodynamic surrogate of efficacy.

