### Criteria for Pharmacodynamic Similarity Acceptance

Rabies Virus Neutralizing Activity plotted against time will be created. Pharmacodynamic parameters for SYN023 mAb will be estimated using non-compartmental analysis. Cmax, Tmax, AUC0-last, AUC0-inf will be calculated. For the comparison of RIG to SYN023 with RVi and RVa vaccines: The 90% confidence intervals for the ratio of geometric means (RIG/SYN023) must be 80% to 125%. An ANOVA of the ln-transformed AUC0-inf will be run to determine the 90% confidence interval on the difference between treatments. The confidence interval limits derived on the log scale will be back-transformed to the raw AUC scale for comparison to the acceptance criteria.

To investigate any interference of SYN023 to the immune response generated by the vaccine, a non-inferiority test of the AUC14-last between RIG and SYN023 for each vaccine can be performed. The one-sided 90% confidence interval derived on the log transformed AUC from an ANOVA would be compared to the lower acceptance criterion of 80%.

Additionally, a non-inferiority test of the level of RVNA between RIG and SYN023 for each vaccine at selected time points, such as 14 or 28 days, can be performed using a Wilcoxon rank sum approach with a non-inferiority of 10% of the level associated with RIG. Pharmacodynamic efficacy will be defined as RVNA measured above 0.5 IU/mL with RVi and RVa for the duration of the trial and no more than 10% lower for SYN023 compared to RIG at any time point through Study Day 35.

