10.1 Handling of the BLQ and the No Reportable Concentration Values	20

10.2	Handling of the Difference Between the Scheduled and the Actual Sampling Times	20
10.3	Efficacy/Pharmacodynamic Parameters	20
10.4	Statistical Analyses	21
10.4.1	Similarity Acceptance	22
10.4.2	RIG vs. SYN023 Comparison by Timepoint	22
11.	Immunogenicity: Anti-SYN023 Antibodies Analyses	23
11.1	Immunogenicity Parameters	23
11.2	Statistical Analyses	23
12.	Pharmacokinetic Analyses	23
12.1	Handling of the BLQ and the No Reportable Concentration Values	23
12.2	Handling of the Difference Between the Scheduled and the Actual Sampling Times	23
12.3	Pharmacokinetic Parameters	24
12.4	Statistical Analyses	25
13.	Data Handling	25
14.	Handling of Missing Data	25
15.	Software to be Used	25
16.	Reference List	26

LIST OF ABBREVIATIONS

Abbreviation	Term
AE	Adverse event
ALT	Alanine aminotransferase
ALP	Alkaline phosphatase
ANOVA	Analysis of variance
AST	Aspartate aminotransferase
AUC_{0-t}	Area under the concentration- time curve from time 0 to the last measurable concentration (equivalent to AUC _{0-last})
AUC_{0-inf}	Area under the concentration-time curve from time 0 to infinity
AUEC_{0-t}	Area under the effect-time curve above the minimum rabies virus neutralizing activity threshold (0.5 IU/mL) from time 0 to the last measurable concentration
AUEC_{14-t}	Area under the effect-time curve above the minimum rabies virus neutralizing activity threshold (0.5 IU/mL) from time 14 days to the last measurable concentration
BLQ	Below the lower limit of quantitation
BMI	Body Mass Index
CI	Confidence Interval
C_{max}	Maximum observed concentration
Clp	Plasma clearance
Clp/kg	Plasma clearance normalized for the subject body weight in kg
CRF	Case report form
CPK	Creatinine phosphokinase
CSR	Clinical Study Report
CV	Coefficient of variation
ECG	Electrocardiogram
E_{max}	Maximum observed effect
GLM	Generalized Linear Model
HR	Heart Rate
IG	Immune Globulin
IU	International units
K_{el}	Terminal elimination rate constant (equivalent to λ_z)
K_{el Lower}	The actual sampling time where K _{el} calculation begins
K_{el Upper}	The actual sampling time of the last measurable concentration used to estimate the K _{el}
kg	Kilogram
Max	Maximum

MedDRA	Medical dictionary for regulatory activities
Min	Minimum
mL	Milliliter
PD	Pharmacodynamic
PK	Pharmacokinetic
PP	Per Protocol
% \geq 0.5 IU/mL	Percentage of subjects with RVNA values \geq 0.5 IU/mL
PT(INR)	Prothrombin time (international normalized ratio)

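### The SAP has no variable, summary or decision rule for the protocol's efficacy definition (RVNA above 0.5 IU/mL throughout), and its one acceptance criterion barely registers an early or brief gap

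*SAP*

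**What the plan says.** **Protocol.** Section 7.3 states: "Pharmacodynamic efficacy will be defined as RVNA measured above 0.5 IU/mL with RVi and RVa for the duration of the trial". The same definition is in section 2.2 and in the design part of the study abstract. Sections 2.2 and 7.3 add a relative condition: "no more than 10% lower for SYN023 compared to RIG at any time point through Study Day 35". The abstract's efficacy paragraph says: "RVNA of >0.5 IU/mL will be used as a pharmacodynamic surrogate of efficacy".

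**SAP, primary analysis.** Section 5 says: "The primary parameters will be $AUEC_{0-t}$ calculated on RVNA measured above 0.5 IU/mL". Section 10.3 defines that parameter as the "area under the effect-time curve above the minimum rabies virus neutralizing activity threshold (0.5 IU/mL) from time 0 to the last measurable concentration". Section 10.4.1 contains the only acceptance criterion: the 90% interval for the RIG/SYN023 ratio from the "ln-transformed $AUEC_{0-t}$ must be within 80.00% to 125.00"%.

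**SAP, the 0.5 IU/mL threshold as a response measure.** Section 10.4 plans listings, individual and mean curves, and descriptive statistics over time that include "the percentage of subjects with RVNA values above 0.5 IU/mL [% > 0.5 IU/mL". The abbreviation list gives the same quantity as "Percentage of subjects with RVNA values \geq 0.5 IU/mL".

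**SAP, changes.** Section 4 records the renaming of the pharmacodynamic parameters and the removal of AUC0-inf. It does not mention the 0.5 IU/mL definition.

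**The concern.** The documents treat 0.5 IU/mL as the reference level for an adequate response (Protocol 1.6). The passive antibody is there to hold that level until the vaccine response arrives (Protocol 1.1 and 1.5). The protocol turns this into an efficacy definition, but the SAP has nothing that evaluates it over the course of the trial.

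Two consequences follow. The study report could not state from a prespecified analysis whether the definition was met, or by how many subjects. And a passed AUEC0-t criterion could be read as similar protection, although that area is driven mostly by the weeks of vaccine response and gives time below 0.5 IU/mL no weight.

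**Working it through.** **No planned figure to reproduce.** Neither document states a power or sample size for the 0.5 IU/mL definition. The power of 0.838 in Protocol 7.7 concerns a mean difference in RVNA. It reproduces as 0.8376 (two-sample t-test, n = 40 per group, SD 3, difference 2, with two-sided alpha 0.05 assumed because none is given), and the point does not rest on it.

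**1. Do by-visit percentages determine the share above 0.5 throughout?** SAP 10.3 has 10 samples, so k = 9 are post-dose. If a proportion p is above 0.5 at each visit, the proportion above at all k lies between max(0, 1 − k(1 − p)) and p. The values of p are assumptions.

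| p per visit | lower bound | upper bound | if visits were independent (p^9) |
|---|---|---|---|
| 0.99 | 1 − 9 × 0.01 = 91% | 99% | 91.4% |
| 0.95 | 1 − 9 × 0.05 = 55% | 95% | 63.0% |
| 0.90 | 1 − 9 × 0.10 = 10% | 90% | 38.7% |

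The lower bound is an extreme, with different subjects failing at each visit. The by-visit figures do not settle the question.

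**2. How much of AUEC0-112 comes from Days 0-7?** Inputs: mean RVNA for 0.3 mg/kg in Protocol Table 1.5-1 (0, 2.70, 3.68 and 4.44 IU/mL on Days 0, 1, 3 and 7), then a linear rise to an assumed plateau V at Day 14, held to Day 112. Area above 0.5 by linear trapezoids:

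- Days 0-1: 2.20² / (2 × 2.70) = 0.90
- Days 1-3: (2.20 + 3.18) / 2 × 2 = 5.38
- Days 3-7: (3.18 + 3.94) / 2 × 4 = 14.24
- Days 0-7 in total: 20.5 IU·day/mL
- Days 7-14: 7 × (3.94 + V − 0.5) / 2
- Days 14-112: 98 × (V − 0.5)

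If RVNA is instead zero through Day 7 and then rises linearly to V at Day 14, Days 0-14 contribute only 7(V − 0.5)² / (2V).

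| V (IU/mL) | Days 7-14 | Days 14-112 | AUEC0-112 | share of Days 0-7 | AUEC0-112, no activity to Day 7 | as % of reference |
|---|---|---|---|---|---|---|
| 20 | 82.0 | 1911 | 2014 | 1.0% | 66.5 + 1911 = 1978 | 98.2% |
| 10 | 47.0 | 931 | 999 | 2.1% | 31.6 + 931 = 963 | 96.4% |
| 5 | 29.5 | 441 | 491 | 4.2% | 14.2 + 441 = 455 | 92.7% |

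If only the SYN023 arm lost this activity, the RIG/SYN023 point ratio would be 100/98.2 = 101.8%, 100/96.4 = 103.7% or 100/92.7 = 107.9%. If only the RIG arm lost it, the ratio would be 98.2%, 96.4% or 92.7%.

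**3. Late gap, same profiles.** Set Days 84 and 112 to 0.3 IU/mL. The area from Day 42 to Day 84 becomes 42(V − 0.5)² / (2(V − 0.3)), and nothing is added after that. For V = 20: 20.5 + 82.0 + 28 × 19.5 + 405.3 = 1054, which is 52% of 2014. For V = 10 and V = 5 the results are 53% and 54%. A prolonged late gap therefore moves AUEC0-t well outside the limits.

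**4. Do the other planned analyses cover the early period?** AUEC0-7 and AUEC0-14 enter the ANOVA in SAP 10.4.1, but that section specifies ratios and 90% intervals only for AUEC0-t, AUEC14-t and Emax. SAP 10.4.2 gives ratios with 90% and 95% intervals at each visit from Day 1, without an acceptance limit. Both analyses take logarithms of values that can be zero: AUEC0-7 is zero for a subject never above 0.5 by Day 7, and SAP 10.1 sets values below quantification to zero. No rule is given, so by default the subjects with the least activity would drop out of these comparisons.

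**The case against.** The strongest reply has five parts.

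- **The protocol does not say per subject.** This is correct. A reader might infer that a subject-level endpoint was promised and then withdrawn, but the wording does not support that. The relative condition in the same sentence compares groups, so a group-level reading is natural. On that reading, too, the SAP attaches no decision rule to 0.5 IU/mL.
- **The SAP kept the protocol's acceptance criterion.** This is also right. Protocol 7.3 already uses an AUC ratio with limits of 80% to 125%, and SAP 10.4.1 carries this over to AUEC0-t. Protocol 3.6.1 adds that this is not an efficacy trial. It would be wrong to say that the area measure was swapped in for the threshold definition; the threshold definition was left without an analysis.
- **Gaps would be visible anyway.** This is partly true. Listings, curves, by-visit percentages, AUEC0-7 and the by-visit ratios would show an early deficit descriptively. None of them gives a defined summary of staying above 0.5, and none has a criterion.
- **The numbers are extreme.** The plateaus are assumptions. The 20 IU/mL in Protocol 7.7 is described as a mean for SYN023 and should not be taken for a vaccine plateau. The 80% to 125% limits apply to a confidence interval, so a small shift in the point ratio does not prove that the criterion would be met. Nor do the documents suggest an early SYN023 failure: Table 1.5-1 shows means of 2.70 to 4.44 IU/mL on Days 1 to 7, and Protocol 1.5 reports all volunteers at this dose above 0.5 for at least 35 days. The calculation shows what the criterion can detect and does not forecast a result.
- **The cut-off conflict is trivial.** Largely so. The operative statements in both documents say above or >. The conflicting sign is in one SAP abbreviation entry (the protocol's other uses describe Phase 1 results), and it matters only for a value of exactly 0.5.

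**Conclusion.** The point holds in a limited form. The protocol's definition of pharmacodynamic efficacy has no variable, summary or decision rule in the SAP, and SAP 4 does not say so. The acceptance criterion that remains is nearly insensitive to early or brief gaps: Days 0-7 supply about 1% to 4% of AUEC0-112, and complete loss of activity through Day 7 lowers the area by about 2% to 7%. These sizes rest on the Phase 1 means in Table 1.5-1, assumed plateaus of 20 to 5 IU/mL and a linear rise between Days 7 and 14. The 55% to 95% range rests on an assumed 95% at each visit.

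A reader might go further and infer that AUEC0-t cannot reveal any gap. The documents do not support that, because a prolonged late gap roughly halves the area in the same profiles. The > versus ≥ discrepancy is an editing matter. The change should be made before database lock; data collection and the primary analysis stay as planned.

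**What to change.** 1. In SAP 10.3 and 10.4, define a subject-level indicator: RVNA above 0.5 IU/mL at every scheduled post-dose visit from Day 1 to Day 112. Exclude Day 0, because that sample is taken before dosing in subjects without previous rabies vaccination. Derive it also for Days 1-7 and Days 14-112 separately.
2. State a missing-visit rule. For example, any observed value not above 0.5 makes the subject a non-responder, and results are shown once with missing visits ignored and once with missing visits counted as failure. The rule is needed because SAP 6.2 admits subjects followed for only 28 days and SAP 14 uses observed data only.
3. Report n/N with an exact confidence interval per arm, and the SYN023-minus-RIG difference with a confidence interval for each vaccine.
4. Use > 0.5 throughout, as in the operative text of both documents, and correct the SAP abbreviation entry.
5. Do not present AUEC0-t similarity alone as similarity of protection.

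If the sponsor prefers not to evaluate the definition, SAP 4 should say so and give the reason.

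**Cost:** SAP wording and one derived variable from samples already scheduled, with no protocol change to the cut-off. The downside is one more reported result, which may look less favourable than the AUEC ratio.
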